### Pre screening diagnosis of S. mansoni infected participants (Cohorts 1 to 3)

Pre screening diagnosis of S. mansoni infection will be done using a single POC-CCA urine cassette test. POC CCA cassettes will be classified as either positive or negative, according to the manufacturer's instructions, with further stratification depending on the strength of the color reaction. Thus, positive cassettes will be classified as + 1 (when result line is easy to see but still weak), + 2 (when result line is dark, but lighter than the control line) or + 3 (when result line is as dark as or darker than the control line). Participants who are positive in the POC-CCA test will be further screened with the aim of:

- Assessing S. haematobium co-infection using the urine filtration technique. A urine sample (about 10 mL) will be filtered through a filter mesh, and the mesh will then be examined under the microscope for S. haematobium egg count. A diagnosis of S. haematobium is defined as positive egg count of S. haematobium in urine ( $> 1$  egg/10 mL of urine) according to WHO classification (WHO, Geneve, Switzerland, 2002) light ( $< 50$  eggs/10 mL of urine) and heavy ( $\geq 50$  eggs/10 mL of urine) infections. Per Section [5.2](#) (Exclusion Criteria), a child infected with both S. mansoni and S. haematobium cannot participate in this study.
- Assessing infection intensity at baseline using the Kato-Katz method: One stool sample will be collected during the pre screening period (Day -28 to Day -1) and the second one within a maximum of 5 days thereafter as baseline. In case the stool collection will not be possible within a maximum of 5 days between the samples, 2 other stool samples could be collected again (maximum 3 times over 28 days). Three Kato-Katz thick smears (41.7 mg) will be prepared from each of the stool samples. Infection intensity (expressed as egg count per gram of stool [epg]) will be calculated for each individual. A diagnosis of S. mansoni is defined as positive egg counts of S. mansoni in stool ( $> 1$  egg/1 occasion) according to the WHO

classification: light (1 to 99 eggs per gram of feces), moderate (100 to 399 eggs per gram of feces) and heavy ( $\geq 400$  eggs per gram of feces) infections.

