## **8.1 Efficacy Assessments and Procedures**

### **8.1.1 Assessment of Primary Efficacy Endpoint**

The primary endpoint of this study is clinical cure rate based on objective assessment of egg counts in Cohort 1. To assess clinical cure in the 4 to 6 years of age children infected with *S. mansoni* (Cohort 1, Treatment Groups 1a and 1b), epg will be quantified 17 to 21 days after treatment, as determined by the Kato-Katz thick smear method described by WHO (2013). The method will be identical to the one used in the Phase II study. Two stool samples will be collected within a maximum of 5 days during the pre screening period (Day -28 to Day -1) as baseline. Two additional stool sample will be collected at the End-of-Study visit, one between 17 and 21 days after dosing, and another one within a maximum of 5 days later to determine efficacy. Three Kato-Katz thick smears will be prepared from each of the stool samples and read under the microscope. To meet the primary efficacy endpoint, a participant must have no *S. mansoni* eggs in any of the Kato-Katz smears collected after the dosing.

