| Primary (mITT) | 
Clinical cure is defined as no parasite eggs in the stool 17 to 21 days after treatment.
 
Egg counts will be determined by the Kato-Katz method: One stool sample will be collected during the pre screening period (Day -28 to Day -1) and the second one within a maximum of 5 days thereafter as baseline. Two additional stool samples will be collected between Day 17 to 21 after dosing to determine efficacy: the first one will be collected within the 17 to 21 day window and the second one within a maximum of 5 days following collection of the 1st sample. Three Kato-Katz thick smears (41.7 mg) will be prepared from each stool sample
 | 
No hypothesis testing will be performed. Point estimates and corresponding two-sided 95% CIs will be determined.
 
Subjects cured of infection during the trial will be labelled as "responders". Responders will be defined as subjects with no parasite eggs (as determined by Kato-Katz method) in the End of Study stool samples, 17 to 21 days after treatment, according to the eCRF page "End of Study (Day 17 to Day 21)". Responders and non-responders will be coded as follows:
 
 For responders, response = 1 For non-responders, response = 0 
The proportion of responders in each cohort will be determined based on a binomial distribution. Exact 95% CIs will be calculated based on the Clopper-Pearson method. The PROC FREQ procedure in SAS will be used with the BINOMIAL and EXACT option for point estimates and corresponding 95% CIs.
 
Point estimates and corresponding 95% CIs will be presented for cure rate, in terms of proportion of responders, by cohort. Response will be listed by cohort and subject. Estimates of cure rate will be presented graphically in the form of forest plots presenting point estimates and 95% CIs.
 
For mITT analysis tables will be presented with imputation and without imputation.
 
Results will be presented for each analysis set.
 | 
If the End of Study Kato-Katz egg count is missing, it will be imputed using the Last Observation Carried Forward (LOCF) approach. Subjects with missing data will be considered non-responders.
 |
| Sensitive (PP) | | | No imputation will be done |
| Sensitive (SAF) | | | No imputation will be done |

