
| | | | |
|---|---|---|---|
| | 
visit, Cohort 4 participants will be asked to provide three additional urine samples (about 10 mL each) on different days between Day 35 and Day 40. Each urine samples will be filtered through a filter mesh. This mesh is then examined under the microscope for S. haematobium egg count.
 | | |
| 
Secondary endpoint: Egg Reduction Rate (ERR) 17 to 21 days after treatment, in children 4 to 6 years of age infected with S. mansoni (Treatment group 1a and 1b)
 | | | |
| 
Primary (mITT)
 | 
ERR from pre treatment to 17 to 21 days after treatment, using parasite egg counts as determined by the Kato-Katz method for Cohort 1.
 | 
The group/collective egg reduction rate will be determined for cohort 1a and 1b as follows:
 
Step 1: Calculate the arithmetic group mean and geometric group mean egg counts (egp) at each visit. The geometric mean is defined as:
 $GM(x_1, \dots, x_n) = e^{(1/n \sum_{i=1}^n \log(x_i+1))} - 1$ 
Where x_i is the egg count for subject i.
 
Step 2: Calculate group ERR for each treatment group and individual ERR
 
 • $ERR_A \text{ (%) } = \text{relative difference expressed in percent between the post-treatment mean egg count and the pre-treatment mean egg count } ((\text{pre-treatment mean egg count} - \text{post-treatment mean egg count}) / \text{pre-treatment egg count})$. • $ERR_G \text{ (%) } = \text{relative difference expressed in percent between the geometric mean post-treatment egg count and geometric mean pre-treatment egg count } ((\text{geometric mean pre-treatment egg count} - \log\text{-transformed post-treatment egg count}) / \text{geometric mean pre-treatment egg count})$. 
In addition: individual ERR (iERR) will be calculated for each patient:
 
 • $iERR \text{ (%) } = \text{relative difference expressed in percent between the post-treatment egg count and the pre-treatment egg count } ((\text{pre-treatment egg count} - \text{post-treatment egg count}) / \text{pre-treatment egg count})$. 
All raw egg counts will be multiplied by 4 in background of EDC system generating egg counts as eggs/gram (mansoni) and eggs/10ml (haematobium) respectively.
 | 
If the End of Study Kato-Katz egg count is missing, it will be imputed using the Last Observation Carried Forward (LOCF) approach. Subjects with missing data will be considered non-responders.
 |

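### The fixed factor of 4 gives eggs per gram for S. mansoni only when six smears are summed; with fewer smears read, epg is understated and ERR can be distorted

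*SAP*

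**What the plan says.** The ERR derivation in SAP 14.2 (Secondary Endpoint Analyses) converts counts with one constant: "All raw egg counts will be multiplied by 4 in background of EDC system generating egg counts as eggs/gram". The constant is applied inside the data capture system, and no condition is attached to it.

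The sampling scheme for Cohorts 1 to 3 is two stools at each of two visits:
- Baseline, Protocol 8.1.1: "Two stool samples will be collected within a maximum of 5 days during the pre screening period (Day -28 to Day -1) as baseline".
- Follow-up, SAP 14.1.1: "Two additional stool samples will be collected between Day 17 to 21 after dosing to determine efficacy".
- Smears, SAP 14.1.1: "Three Kato-Katz thick smears (41.7 mg) will be prepared from each stool sample". Protocol 8.1.1 agrees.

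If the baseline pair cannot be completed in time, the pre-screening text in Protocol section 8 allows a repeat: "2 other stool samples could be collected again". No equivalent is stated for follow-up.

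Individual ERR is the "relative difference expressed in percent between the post-treatment egg count and the pre-treatment egg count". The SAP also reports the share of children whose individual ERR is at least 90%, and it presents the mITT tables both with and without imputation.

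**The concern.** A fixed multiplier is safe only if every child has the same amount of stool examined at every visit. A missing second stool or an unreadable smear reduces the amount examined, but the multiplier stays the same. ERR compares two such counts, so a shortfall at one visit only does not cancel.

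The endpoints at stake are the arithmetic, geometric and individual ERR in the three S. mansoni cohorts. The mITT set, which is the main analysis set, does not require a complete set of smears. SAP 8.2 asks only for a dose, a baseline measurement and no malaria treatment after enrolment.

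**Working it through.** **Inputs.** Smear mass 41.7 mg, three smears per stool, two stools per visit (SAP 14.1.1, Protocol 8.1.1). Factor 4 and the 90% threshold (SAP 14.2). Planned set sizes for group 1a: 95 mITT and 80 per protocol (Protocol 9.2, Table 5).

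**Step 1: reproduce the factor.** To turn a count summed over s smears into eggs per gram, the factor is 1000 / (41.7 × s).

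| Smears read | Stool examined (mg) | Factor needed | Expected epg with ×4, relative to truth |
|---|---|---|---|
| 6 | 250.2 | 3.997 | 1.00 |
| 5 | 208.5 | 4.796 | 0.83 |
| 4 | 166.8 | 5.995 | 0.67 |
| 3 (one stool) | 125.1 | 7.994 | 0.50 |

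The plan's 4 is reproduced by the six-smear sum. Applied to a mean per smear, the factor would have to be 1000/41.7 = 23.98. The sum is therefore the only reading under which the SAP's sentence yields eggs per gram.

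**Step 2: individual ERR, full baseline, one follow-up stool.** The expected post-treatment epg is halved, so the reported value is 1 − (1 − iERR)/2. A true 50% reads 75%, 80% reads 90%, 90% reads 95%, and 95% reads 97.5%.

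An invented example: 25 eggs over six smears at baseline is 100 epg. Five eggs over six smears afterwards is 20 epg, so iERR is 80%. One stool would contain 2.5 of those eggs on average, giving 10 epg and iERR 90%. With 2 eggs the report is 8 epg and 92%; with 3 eggs it is 12 epg and 88%.

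**Step 3: the reverse case.** With one baseline stool and a full follow-up, the baseline is halved and 1 − iERR doubles, so a true 90% reads 80%. If both visits have one stool, the error cancels in iERR.

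**Step 4: group arithmetic ERR.** Let a share f of children have one follow-up stool, with a full baseline and average post-treatment counts. Reported ERR = 1 − (1 − ERR)(1 − f/2).

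The documents give no one-stool rate, so f is assumed. As an upper end I take every child whom the plan allows to be in mITT but not per protocol: (95 − 80)/95 = 15.8%.
- f = 5%, true 90%: 1 − 0.10 × 0.975 = 90.25%.
- f = 15.8%, true 90%: 1 − 0.10 × 0.921 = 90.8%.

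The geometric ERR moves in the same direction, because a smaller non-zero post-treatment count lowers the geometric mean.

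**The case against.** A reader might infer that the bias always inflates ERR. The documents do not support that, for four reasons.

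- **The raw count is not defined.** SAP 14.2 never says that it is a sum, and it describes the listing in terms of mean counts. If ×4 were applied to a mean per smear, epg would be one sixth of the truth at every visit. Arithmetic and individual ERR would then be unchanged. How the data capture system handles an incomplete set cannot be seen, because its specification is not among the documents.
- **One stool of two might be treated as missing.** Protocol 9.4.1 says that children in mITT but not per protocol need imputation, and SAP 8.2 lists missing end-of-study stools as a per-protocol exclusion. Carrying the baseline forward gives that child an ERR of 0, which understates efficacy.
- **Baseline can also be incomplete.** Re-collection is permitted, not required, and mITT asks only for a baseline measurement.
- **The halving holds on average.** It would be wrong to say that every one-stool child with a true iERR of 80% to 90% passes the threshold; in the example above, 3 eggs leaves the child at 88%.

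It is also tempting to take the protocol's 20% non-evaluable rate as f. That allowance covers all exclusions from the per-protocol set, including the 5% for malaria treatment who are already outside mITT.

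These points limit the direction and size of the effect but do not remove the problem. The mITT tables without imputation give carry-forward no role, mITT does not drop one-stool children, and no text scales by smears read. The per-protocol criterion names missing samples, not an unreadable smear within a collected stool.

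**Conclusion.** The point holds in a conditional form. Under the only reading that makes the SAP's sentence true for S. mansoni, the rule gives a wrong epg whenever fewer than six smears are read and the child is analysed as observed. The understatement in expectation is one half with one stool and one sixth with five smears. ERR is overstated if the shortfall is at follow-up and understated if it is at baseline. Follow-up is the likelier place, because only baseline has a stated repeat option.

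At group level the shift is under one percentage point for a true ERR of 90%, with f assumed at 5% to 15.8%. The clearer consequence is for the proportion with iERR of at least 90%: a child with eggs remaining and a true value of about 80% to 90% can be moved to or over the line.

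The effect is confined to a descriptive secondary endpoint. Zero stays zero under any factor, so the primary cure rate does not depend on it. The per-protocol set is largely protected by its exclusion for missing stools.

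**What to change.** In SAP 14.2:
1. Define the S. mansoni raw count as total eggs over all smears read at the visit.
2. Derive epg = 1000 × total eggs / (41.7 × number of smears read) at each visit in the analysis datasets, in place of the constant in the data capture system. This equals about 24 × mean eggs per smear and returns the factor of 4 when six smears are read.
3. State that one stool of two is analysed as observed on this scale and is not treated as missing for carry-forward.

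No new samples are needed. The change does require stool-level or smear-level counts, with the number of smears read, in the database; the documents do not show whether these are stored. SAP 14.2.1 pools derived variables directly with Phase II Cohorts 8 and 9 on the premise that the derivation rules match. The same derivation should therefore be checked for, or applied to, those data before pooling.

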## 9 Statistical Considerations

### 9.1 Statistical Hypotheses

No formal hypothesis testing is planned. Point estimates of the cure rate and two- sided 95% CI will be calculated for all cohorts.

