In Cohort 2, a total of 30 participants 2 to 3 years of age infected with *S. mansoni* will be enrolled to assess consistency of the treatment effect with that in the older age group. As described in Section 4.2.4, the size of Cohort 2 is 30% of that of Treatment group 1a, to be roughly consistent with the distribution of children 2 to 3 years of age (27%) and 4 to 6 years of age (73%) enrolled in the Phase II study, in which no differences in cure rate by age were observed.

In Cohort 3, overall a total of up to 65 participants 3 to 24 months of age infected with *S. mansoni* will be enrolled in the Phase II and Phase III studies. The sample size in either study alone is too small to have adequate precision on the cure rate, thus the results in this Phase III study (Cohort 3) will be pooled with Cohorts 8 and 9 of the ongoing Phase II study (MS200661-0005). In the Phase II Study MS200661-0005, 20 out of 30 planned participants 13 to 24 months of age and 4 out of 10 planned participants 3 to 12 months of age were enrolled in the study. In Cohort 3 of this Phase III study, at least 25 participants 3 to 24 months of age infected with *S. mansoni* (i.e., ~20% of the total number of participants 2 to 6 years of age receiving L-PZQ ODT) will be enrolled. Since the enrollment of this age group from Phase II was lower than planned, more than 25 participants will be enrolled in Phase III Cohort 3 to achieve a total of 65 participants in this age group. This pooled sample will allow a general comparison to assess whether the treatment effect is similar across age groups.

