### 9.4 Statistical Analyses

All endpoints will be analyzed descriptively. Graphs will be produced as appropriate. Descriptive statistics for categorical endpoints will include frequency counts and percentages. For proportion endpoints, the calculation of 95% CIs will be based on the Clopper-Pearson (exact) method.

Descriptive statistics for continuous endpoints will include: number of available observations, mean, standard deviation, median, lower quartile, upper quartile, minimum, and maximum. For continuous endpoints, the 95% CI around the mean will be calculated where applicable.

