#### 9.4.1 Efficacy Analyses

The primary efficacy analysis will be performed on the mITT population of Cohort 1. The primary endpoint of cure rate will be calculated as the percentage of egg-positive participants at baseline who become egg-negative after treatment (as assessed by the Kato-Katz method). The exact 95% CI will be calculated based on the Clopper-Pearson method. Cohorts 2, 3, and 4 will be analyzed similarly.

The secondary endpoint of cure rate by POC-CCA® (Cohorts 1, 2, and 3) will be analyzed in the same manner as the primary endpoint, with proportion cured and its 95% CI.

The secondary endpoint of ERR will be analyzed for each of the cohorts and treatment group (Cohort 1) as group-based ERR (arithmetic and geometric) and as individual ERR (arithmetic and geometric).

Subgroup analyses will also be conducted by severity of infection (light vs. moderate/heavy infection stratification factor), country and gender. In Cohort 4, subgroup analyses will also be done by specific age groups (e.g., 3 months to 24 months of age, 2 to < 4 years of age, 4 to 6 years of age).

Sensitivity analyses may be performed on the ITT population of Cohort 1, to determine the impact of participants requiring malaria treatment, and on the PP population of Cohort 1, to assess the impact of any protocol deviations (such as completing study assessments outside the Day 17 to 21 window).

Analysis of Cohort 3 will be a pooled analysis, including the mITT population from this study and the mITT population for participants 3 to 24 months of age in the Phase II study MS200661-0005 (Cohorts 8 and 9). A logistic regression model with adjustment for study and site variability will be used to estimate cure rate.

Analysis of Cohort 4 will be performed only on the mITT population and using the same methods as for Cohort 1.

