6.3 Final Analysis

Cut-off for analysis: Final database lock.

Responsible party: Triclinium Clinical Development, Merck Healthcare KGaA.

Following completion of the trial, the final trial analyses identified in this IAP will be performed only after the last subject has completed the scheduled assessments of the trial with all trial data in-house, all data queries resolved, and the database locked.

All primary, secondary endpoints and safety endpoints will be analysed.

A data review meeting will be held prior to database lock. In addition, no database can be locked until this IAP has been approved.

7 Changes to the Planned Analyses in the Clinical Study Protocol

The statistical methods as described in the protocol and protocol amendments were adopted. There are no changes to the planned analyses.

Impact of COVID-19 considerations:

This is a single dose study with lean design. Efficacy assessments are taken at home based follow up visits. The impact of COVID-19 on efficacy assessment was deemed low. Missing data and increase in protocol deviations due to COVID-19 are not anticipated, hence no sample size re-estimation is planned, and no change in this IAP is made for COVID-19.

If in rare scenarios COVID-19 is diagnosed for any subjects, the occurrence of this disease will be summarized in the AE tables. If protocol deviation was determined with COVID-19 as the reason, the scenario will be also summarized in protocol deviation table(s).

8 Protocol Deviations and Analysis Populations

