| 
Primary (PP)
 | | | 
No Imputation will be done.
 |

| | | | |
|--|---|---|--|
| | | 
Point and interval estimates of ERR_A, ERR_G and proportion of individuals with $iERR \geq 90\%$ will be presented by treatment group. 95% CIs of these 3 parameters will be calculated by bootstrapping (using SAS procedure SURVEYSELECT). Mean Kato-Katz egg counts will be listed by cohort and subject and time point. Estimates of ERR_A, ERR_G and $iERR$ will be presented graphically in the form of boxplots, by cohort.
 
Results will be presented for each analysis set.
 | |
| Secondary endpoint: Egg Reduction Rate (ERR) in children 2 to 3 years of age and in infants and toddlers 3 months to < 24 months of age infected with S. mansoni (Cohorts 2 and 3, respectively) and in children 3 months to 6 years of age infected with S. haematobium (Cohort 4). | | | |
| Primary (mITT) See 14.1.2 for details about analysis for participant 3 to 24 months of age (Cohort 3). | ERR from pre treatment to 17 to 21 days after treatment, using parasite egg counts as determined by the Kato-Katz method for Cohorts 2 and 3 and the urine filtration method for Cohort 4. Additionally, for Cohort 4b participants ERR from baseline to 35 to 40 days after treatment, using parasite egg counts as determined by the urine filtration method, | Same as Cohort 1 (Secondary analysis). | 
If the End of Study egg count is missing, it will be imputed using the Last Observation Carried Forward (LOCF) approach. Subjects with all post-baseline egg counts missing will be considered non-responders.
 
For cohort 4b, if egg counts is missing only at Extended Follow-up visit, it will be imputed by taking the value from End-of-study visit.
 |
| Secondary endpoint: cure rate as demonstrated with use of the commercially available point-of-care circulating cathodic antigen (POC-CCA®) test (Cohorts 1, 2, and 3). | | | |

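### The SAP bootstraps the confidence interval for the proportion of children with iERR ≥ 90%, where the protocol's rule is Clopper-Pearson; near 100% the bootstrap interval collapses and under-covers

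*SAP*

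**What the plan says.** SAP 14.2 (ERR in treatment groups 1a and 1b) defines an arithmetic group ERR (ERR_A), a geometric group ERR (ERR_G) and an individual ERR. It asks for point and interval estimates of the two group rates and of the share of children at or above a 90% individual reduction, then states that "95% CIs of these 3 parameters will be calculated by bootstrapping (using SAS procedure SURVEYSELECT"). It gives no bootstrap type, number of resamples or rule for results at the boundary. The ERR row for Cohorts 2, 3 and 4 takes over the same methods: "Same as Cohort 1 (Secondary analysis").

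Protocol 9.4 gives a general rule with no exception: "For proportion endpoints, the calculation of 95% CIs will be based on the Clopper-Pearson (exact) method". Protocol 9.4.1 describes the ERR analysis "as group-based ERR (arithmetic and geometric) and as individual ERR (arithmetic and geometric") and does not name a 90% cut-off. SAP Section 7 states: "There are no changes to the planned analyses". For the cure rate, the SAP itself specifies Clopper-Pearson through PROC FREQ.

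**The concern.** A bootstrap is reasonable for ERR_A and ERR_G, which are ratios of means of skewed counts. It is a poor choice for a binomial proportion close to 1. If all n children succeed, the sample holds nothing but successes, so every resample returns 100% and the reported interval is the single point 100%.

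A result of that kind is plausible here. A cured child has no eggs at follow-up and therefore an iERR of 100%, so within one analysis set the share with iERR ≥ 90% cannot be below the cure rate. Protocol 4.2.3 reports Phase II cure rates of 86% and 90% for the two best L-PZQ doses.

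Cohorts 2 and 3 are small and exist to show whether the effect is consistent with that in older children. A zero-width interval from 30 children would claim certainty that the data cannot support. It would also stand beside exact cure-rate intervals with which it is not comparable.

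**Working it through.** **Inputs**
- Confidence level: 95%, two-sided (Protocol 9.1).
- Cohort 2: n = 30 (Protocol 9.2).
- Cohort 3: the pooled target is 65 and Phase II enrolled 20 + 4 = 24 (Protocol 9.2), so n = 65 − 24 = 41.
- True proportion p with iERR ≥ 90%: not given. Assumed range 0.86 to 0.99, starting at the lower Phase II cure rate quoted above.
- Bootstrap type: not given. Percentile assumed.

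**Check on the plan's own figures.** The Clopper-Pearson lower limit is the 2.5% quantile of Beta(x, n − x + 1). For 76/95 this gives 70.5%, and for 36/43 the full interval is 69.3 to 93.2%. Both agree with Protocol 9.2.

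**Bootstrap interval.** Resampling n children from a sample with x successes makes the resampled count Binomial(n, x/n). The percentile limits are the 2.5% and 97.5% quantiles of that distribution divided by n. At x = n both equal 100%.

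| Result | Bootstrap 95% CI | Exact 95% CI |
|---|---|---|
| 30/30 | 100 to 100 | 88.4 to 100 |
| 29/30 | 90.0 to 100 | 82.8 to 99.9 |
| 41/41 | 100 to 100 | 91.4 to 100 |
| 40/41 | 92.7 to 100 | 87.1 to 99.9 |

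**Coverage.** This is the sum, over every x whose interval contains p, of the Binomial(n, p) probability of x. The chance of a zero-width interval at 100% is pⁿ.

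Example, n = 30 and p = 0.95: the interval misses p when x = 30 (0.95³⁰ = 21.5%) and when x ≤ 24 (0.3%). Coverage is 100 − 21.5 − 0.3 = 78.2%.

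| True p | n = 30: zero width | bootstrap | exact | n = 41: zero width | bootstrap | exact |
|---|---|---|---|---|---|---|
| 0.86 | 1% | 93% | 97% | 0.2% | 92% | 96% |
| 0.90 | 4% | 95% | 99% | 1% | 92% | 97% |
| 0.93 | 11% | 88% | 98% | 5% | 93% | 98% |
| 0.95 | 21% | 78% | 98% | 12% | 87% | 98% |
| 0.97 | 40% | 59% | 99% | 29% | 71% | 99% |
| 0.98 | 55% | 45% | 98% | 44% | 55% | 99% |
| 0.99 | 74% | 26% | 99.7% | 66% | 34% | 99% |

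A simulation with 4,000 trials of 2,000 resamples agreed within about 1.5 percentage points.

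**Sensitivity**
- Sample size: applying the 5% antimalarial loss that the protocol assumes for Cohorts 1 and 4 gives n of about 28 and 39. Bootstrap coverage is then 76% and 85% at p = 0.95.
- Larger groups at p = 0.98: 70% at n = 60 (Cohort 4, final dose), 73% at n = 65 (pooled 3 to 24 months) and 84% at n = 95 (group 1a, mITT).
- Bootstrap type: basic and normal-type intervals collapse in the same way at x = n and do no better overall.

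**The case against.** The strongest reply is that the damage depends on a proportion the documents never give. Between 0.86 and 0.92 the shortfall is mostly modest: coverage is 87 to 95% at n = 30 and 85 to 94% at n = 41, and at 0.86 to 0.90 a zero-width interval has a chance of at most 4%. In Cohort 3 the proportion may also lie close to the cure rate. Six 41.7 mg smears make about 0.25 g, so with counts summed and multiplied by 4 the smallest non-zero result is 4 eggs per gram. A child still shedding eggs then reaches 90% only from a baseline of at least 4/0.1 = 40 eggs per gram, and Protocol 4.2.6 expects only light infections (1 to 99) in that cohort. This stands. It limits how often the fault shows, but does not exclude 95% or more, because the cure rate itself may be that high.

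Imputation helps in part. A missing follow-up count is replaced by the baseline count, so iERR = 0 and an n/n result cannot occur. But the SAP also asks for mITT tables without imputation and a per-protocol analysis with none.

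The protocol does not name this proportion, so the conflict is with its general rule for proportion endpoints, not with a rule written for this parameter. The rule admits no exception, and the SAP gives no reason to depart from it.

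Finally, the endpoint is secondary and descriptive, and the cure rate, which carries the consistency question, already has exact intervals. That lowers the priority. But since no test is planned, the intervals are the only statement of uncertainty.

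**Conclusion.** The concern holds. The SAP specifies an interval method for a binomial proportion that departs from the protocol's general rule without declaring it, and that method fails where this proportion may well lie.

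The collapse at n/n is certain and does not depend on the bootstrap type among those tried. The coverage figures assume a percentile bootstrap and a true proportion that the documents do not supply. The loss is serious from about 95% upward in groups of 30 to 41: 78% and 87% at a true 95%, falling to 45% and 55% at a true 98%. At 90% or below it is mostly small. With one failure the interval is not degenerate, but its lower limit is too high by 90.0 − 82.8 = 7.2 points at 29/30.

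This should be changed. It does not affect the primary endpoint.

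**What to change.** In SAP 14.2, restrict the bootstrap to ERR_A and ERR_G, and state that the proportion with iERR ≥ 90% has a Clopper-Pearson exact 95% CI in every treatment group and in the pooled 3 to 24 month tables. In the same edit, state the bootstrap type, number of resamples and seed for ERR_A and ERR_G. Those two intervals also degenerate if every follow-up count is zero, so say how that case will be reported.

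The cost is one SAP sentence for the proportion and one PROC FREQ call of the kind already specified for the cure rate. No new data are needed. The intervals become somewhat wider, with coverage of at least 95% at every true proportion checked from 0.80 to 0.99. SAP Section 7 can then stand on this point.
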